## 7.2 Randomization

The allocation of IMP to treatment number will be done according to a randomization schedule produced by an independent statistician. The randomization schedule will be held centrally and not divulged to any other person involved in the study until the database has been locked and unblinding authorized by the relevant GW personnel. For access to blinded treatment assignment, see Section 8.5.

The randomization will be stratified by age group (1–6 years, 7–11 years, 12–17 years and 18–65 years).

# 8 TREATMENT PROCEDURES

# 8.1 Investigational Medicinal Product Dosage, Administration and Schedule

The use of placebo in the current study was deemed necessary to determine the efficacy and safety of the current intervention, since the best proven intervention had already been tried or may be given as an adjuvant treatment, failing to fully alleviate the patient's symptoms. For details regarding IMP formulations, see Section 5.

Patients will be assigned to receive GWP42003-P 25 mg/kg/day, GWP42003-P 50 mg/kg/day, placebo 25 mg/kg/day dose volume equivalent, or placebo 50 mg/kg/day dose volume equivalent at a 2:2:1:1 ratio. The placebo groups will be pooled for the analyses of efficacy.

## 8.1.1 Dose Administration

The IMP will be administered by the patient or their caregiver twice each day (morning and evening) using the syringe(s) provided and may be taken with other concomitant medications, as directed by the investigator.

Patients may not be randomized into the study if using a gastrostomy/nasogastric tube, unless the patient is able to still take medication orally. Dosing through gastrostomy/nasogastric tubes may be allowed after consultation with the GW medical monitor. Alteration in dosing frequency may also be considered after consultation with the GW medical monitor.

## 8.1.2 Dose Escalation and Dose Adjustments

All patients will be weighed during Visit 3 and the daily volumes of IMP solution to be taken during the maximum four-week titration period and for the remainder of the blinded phase maintenance period will be calculated via the IVRS and the dosing regimen provided to the patient and/or caregiver. Doses may be altered during the OLE according to changes in patient weight. Further information on dispensing procedures will be provided in a separate Pharmacy Manual.

Titration from 0–25 mg/kg/day will begin at 5 mg/kg/day and will be increased in increments of 5 mg/kg/day every two days (patients will remain on each dose level for two days before they progress on to the next dose). Titration from 25–50 mg/kg/day will continue at smaller increments of 2.5 mg/kg/day every two days.

Table 8.1.2-1Dose Titration Regimen*			
Day	Dose Level 1 (25 mg/kg/day)	Dose Level 2 (50 mg/kg/day)	
1	5.0 mg/kg	5.0 mg/kg	
2	5.0 mg/kg	5.0 mg/kg	
3	10.0 mg/kg	10.0 mg/kg	
4	10.0 mg/kg	10.0 mg/kg	
5	15.0 mg/kg	15.0 mg/kg	
6	15.0 mg/kg	15.0 mg/kg	
7	20.0 mg/kg	20.0 mg/kg	
8	20.0 mg/kg	20.0 mg/kg	
9	25.0 mg/kg	25.0 mg/kg	
10	25.0 mg/kg	25.0 mg/kg	
11	25.0 mg/kg	27.5 mg/kg	
12	25.0 mg/kg	27.5 mg/kg	
13	25.0 mg/kg	30.0 mg/kg	
14	25.0 mg/kg	30.0 mg/kg	
15	25.0 mg/kg	32.5 mg/kg	
16	25.0 mg/kg	32.5 mg/kg	
17	25.0 mg/kg	35.0 mg/kg	
18	25.0 mg/kg	35.0 mg/kg	
19	25.0 mg/kg	37.5 mg/kg	
20	25.0 mg/kg	37.5 mg/kg	
21	25.0 mg/kg	40.0 mg/kg	
22	25.0 mg/kg	40.0 mg/kg	
23	25.0 mg/kg	42.5 mg/kg	
24	25.0 mg/kg	42.5 mg/kg	
25	25.0 mg/kg	45.0 mg/kg	
26	25.0 mg/kg	45.0 mg/kg	
27	25.0 mg/kg	47.5 mg/kg	
28	25.0 mg/kg	47.5 mg/kg	
29	25.0 mg/kg	50.0 mg/kg	

IMP is to be taken twice daily. Total daily doses are shown.

Each patient will take their first dose of IMP at Visit 3 (Day 1) and their final maintenance dose of IMP at Visit 10 (Day 113). If an unacceptable AE develops at any time during the titration period, dosing should initially be suspended or amended, at the investigator's discretion, until the event has resolved. During the maintenance period, patients should continue on a stable dosing regimen at the target Dose Level. If that dose becomes poorly tolerated or an AE occurs (e.g., somnolence, transaminase elevation **not meeting** withdrawal criteria specified in Section 10 and Section 12.8), the investigator may consider temporarily or permanently reducing the dosage for the remainder of the maintenance period following discussion with the GW medical monitor. It is recommended that patients with poor tolerability have their daily dose reduced by 10 mg/kg every seven days unless, in the investigator's opinion, smaller or

larger or more rapid dose reductions are clinically indicated. Where possible, the patient should be encouraged to return to the target Dose Level.

Patients entering the OLE will first complete a two-week blinded transition phase. OLE IMP will be titrated up to 25 mg/kg/day whilst blinded IMP is **simultaneously** tapered down to zero. All patients will complete the transition and enter the OLE taking 25 mg/kg/day GWP42003-P.

Following completion of the blinded transition patients may complete a three-week titration up to a target dose of 50 mg/kg/day. Beginning at 25 mg/kg/day the dose will increase in increments of 2.5 mg/kg/day every two days.

Table 8.1.2-2	Blinded Transition					
Day Blinded	Patients randomized to 25 mg/kg/day group				Patients randomized to placebo group	
Transition/OLE	Blinded	Open-label	Blinded	Open-label	Placebo	Open-label
1	25	0	50	0	0	0
2	22.5	0	45	0	0	0
3	20	5	40	5	0	5
4	17.5	5	35	5	0	5
5	15	10	30	10	0	10
6	12.5	10	25	10	0	10
7	10	15	20	15	0	15
8	7.5	15	15	15	0	15
9	5	20	10	20	0	20
10	2.5	20	5	20	0	20
11	0	25	0	25	0	25
12	0	25	0	25	0	25
13	0	25	0	25	0	25
14	0	25	0	25	0	25

Table 8.1.2-2 is an example of the OLE transition (Visit B1 to Visit B2) for patients transitioning from each group of the randomized phase.

Following completion of the blinded transition patients may complete a three-week titration up to a target dose of 50 mg/kg/day. Beginning at 25 mg/kg/day the dose will increase in increments of 2.5 mg/kg/day every two days (Table 8.1.2-3).

Table 8.1.2-3OLE Titration Sche	e 8.1.2-3 OLE Titration Schedule		
OLE Day	Daily Dose (mg/kg/day)		
15 (Visit B2)	26.25 a		
16	27.5		
17	30		
18	30		

Table 8.1.2-3OLE Titration Schedule		
OLE Day	Daily Dose (mg/kg/day)	
19	32.5	
20	32.5	
21	35	
22	35	
23	37.5	
24	37.5	
25	40	
26	40	
27	42.5	
28	42.5	
29	45	
30	45	
31	47.5	
32	47.5	
33	50	
34	50	
35	50	
36 (Visit B3)	50	

a Derived from an AM dose based on 25 mg/kg/day and a PM dose based on 27.5 mg/kg/day.

Patients who do not enter the OLE study at Visit 10 or withdraw early will have their dose of IMP tapered gradually (10% each day) over a period of 10 days unless continued dosing is not possible due to an AE. Patients not entering the OLE will return used and unused IMP to the clinic at Visit 11.

## 8.2 Concomitant Therapy

It is theoretically possible that GWP42003-P may modify the metabolism of other drugs (including AEDs) administered concurrently and there remains the possibility of pharmacological interactions between GWP42003-P and other concurrently administered drugs. Doses of any concomitant AEDs must have been stable for at least four weeks prior to screening and must remain stable throughout the blinded study period. If during the blinded or OLE phase plasma concentrations of concomitant AEDs are found to be altered following administration of IMP, or if there are side-effects suspected of being related to an elevation in the concomitant AED concentration, the investigator must contact the GW medical monitor to discuss best management. Decisions should be based on clinical symptoms and not plasma levels of AEDs. Further information on drug interactions can be found in the IB. Concomitant AED dose reductions are permitted on clinical grounds (e.g., due to AEs or transaminase elevations **not meeting** withdrawal criteria specified in Section 10 and Section 12.8) following discussion with the GW medical monitor.

Additional new AEDs (including oral mTOR inhibitors) are not allowed to be added during the randomized phase of the trial but may be considered on a case-by-case basis for the OLE phase in accordance with local licensing and after consultation with the GW medical monitor.

The use of rescue medication is allowed when necessary. Any medication, other than the IMP, taken during the study must be recorded on the Case Report Form (CRF).

Any non-pharmacological therapies (e.g., ketogenic diet, vagus nerve stimulation) must also be stable up to four weeks prior to screening and throughout the duration of the study.

## 8.3 Prohibited Therapy During Study Period

The following medications are prohibited for the duration of the study beginning from acquisition of patient consent/assent. However, any patients taking these medications after randomization should not be withdrawn from the study unless there are safety concerns. If applicable, the possible effects of these medications on the primary endpoint will be considered during the assessment of the evaluable period (see Section 13.6.1).

- Any new medications or interventions for epilepsy (including ketogenic diet and vagus nerve stimulation) or changes in dosage.
- Recreational or medicinal cannabis or synthetic cannabinoid-based medications (including Sativex®).
- Any other IMP taken as part of a clinical trial.

Care should be taken with drugs, or their metabolites, that are cytochrome P450 2C19 substrates, such as N-desmethylclobazam. Care should also be taken with drugs, or their metabolites, that are solely or primarily metabolized by UDP-glucuronosyltransferase 1A9 and 2B7.

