# Figure 9.2.17.4-1Flow Diagram for Identifying and Evaluating Clinical Trial
Adverse Event Data Through Systematic Categorization,
Tabulation and Analysis which can Illuminate an Abuse
Potential Signal (for Patients 12 Years of Age and Older)

#### 10 WITHDRAWAL

In accordance with the Declaration of Helsinki, the ICH Tripartite Guideline for GCP Topic E6(R2), the U.S. FDA regulations relating to good clinical practice and clinical trials, the European Union (EU) Clinical Trials Directive, the EU Good Clinical Practice (GCP) Directive and/or other applicable regulations, a patient has the right to withdraw from the study at any time and for any reason without prejudice to his or her future medical care by the physician or at the institution.

The patient must be withdrawn from the study if any of the following apply:

- Administrative decision by the investigator, GW, or a Regulatory Authority.
- Pregnancy.
- Protocol deviation that is considered to compromise potentially the safety of the patient.
- Withdrawal of patient consent/assent.
- Withdrawal of parent(s)/legal representative consent.
- ALT or AST > 3 × ULN with the appearance of fatigue, nausea, vomiting, right upper quadrant pain or tenderness, fever, rash, and/or eosinophilia (> 5%).
- ALT or AST  $> 8 \times ULN$ .
- ALT or AST  $> 5 \times$  ULN for more than two weeks.
- ALT or AST >  $3 \times$  ULN and (TBL >  $2 \times$  ULN or INR > 1.5).
- Lost to follow-up.

Note: Prior to withdrawal for the transaminase elevations noted above, the investigator may choose to confirm the transaminase elevations by repeating the following laboratory tests within 24 to 48 hours: ALT, AST, TBL, INR, %eosinophils, gamma-glutamyl transferase and alkaline phosphatase. Should the above transaminase elevation criteria be confirmed, the patient must be withdrawn from the trial. In cases where the transaminase elevation withdrawal criteria are not met or confirmed, the dose of IMP or a concomitant AED with known hepatotoxicity should be reduced following discussion with the GW medical monitor.

Patients may also be withdrawn from the study for any of the following:

- Did not meet eligibility criteria.
- Patient non-compliance.
- AE (including clinically significant laboratory result) which, in the opinion of the investigator, would compromise the continued safe participation of the patient in the study.

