- Suicidal ideation or behavior of type 4 or 5 during the treatment period, as evaluated with the C-SSRS.
- Any evidence of drug abuse or diversion.
- General anesthesia (blinded phase only).
- Addition of a new AED (blinded phase only).

Should a patient request or decide to withdraw from the study, all efforts must be made to complete all assessments of the End of Treatment/Withdrawal Visit (see Section 9.1.1.10 for withdrawals within the double-blind phase and Section 9.1.2.10 for withdrawals within the OLE phase). All observations should be reported as thoroughly as possible up to the date of withdrawal. Patients withdrawing due to an AE should be followed up according to Section 12.7. All information should be reported in the applicable CRF pages (refer to Section 9.2). Wherever possible, a post-study follow-up visit should take place 28-days after last dose of IMP (refer to Section 9.1.1.12 and Section 9.1.2.13). If withdrawing patients decline to give a reason for withdrawal of consent, the investigator must respect the patient's wishes.

Study Code: GWEP1521 EudraCT Number: 2015-002154-12 Protocol V8 23Apr19

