5.5.3 Secondary Efficacy Endpoints

5.5.3.1 Key Secondary Efficacy Endpoints

5.5.3.1.1 1st Key Secondary Endpoint: TSC-associated Seizure Treatment

Responders (≥50% Reduction in TSC-associated Seizure Frequency)

Blinded Phase:

The proportion of patients considered treatment responders, defined as those with a $\geq 50\%$ reduction in TSC-associated seizure frequency from baseline during the treatment period, for patients who have not withdrawn from the trial during the treatment period, will be summarized by treatment arm and analyzed using a Cochran–Mantel–Haenszel (CMH) test stratified by age group.

The proportion of patients who are considered treatment responders, the difference in proportions along with the 95% CI for the difference, the estimated odds ratios (GWP42003-P arms vs. placebo), 95% CI for the odds ratios, and the p-values from the CMH test will be presented. If no patients in a particular treatment arm are considered responders then the odds ratio and 95% CI for the odds ratio will not be calculated.

The analysis will be performed on the ITT analysis set and repeated on the PP analysis set.

Sensitivity analyses will be performed on the ITT analysis set, repeating the above analysis, using data for the maintenance period only, the titration period and during each 4 weeks of the maintenance period (Week 1 to 4, Week 5 to 8 and Week 9 to 12 of the 12 week maintenance period).

Analyses on the maintenance period, titration period and by each 4 weeks of the maintenance period will include only patients who have at least 7 days of seizure data within each period.

Open-label Extension:

Descriptive summaries described above for the blinded phase will be repeated for OLE periods. However, for the OLE periods, withdrawn patients may be considered responders.

5.5.3.1.2 2nd Key Secondary Endpoint: Subject/Caregiver Global Impression of Change

Blinded Phase:

The SGIC and CGIC comprise the following questions to be rated on a 7-point scale:

CGIC:

- Since your child started treatment, please assess the status of your child's overall condition (comparing their condition now to their condition before treatment) using the scale below.

SGIC:

- Since you started treatment, please assess the status of your overall condition (comparing your condition now to your condition before treatment) using the scale below.

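### Protocol 8.3 and 10 do not give one rule for a patient who adds an AED in the blinded phase, and the SAP lets the site's withdrawal decision settle that patient's responder status

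*Protocol*

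**What the plan says.** - **Protocol 8.2** states that "Additional new AEDs (including oral mTOR inhibitors) are not allowed to be added during the randomized phase of the trial". It does not say what follows if one is added.
- **Protocol 8.3** includes among prohibited therapies "Any new medications or interventions for epilepsy (including ketogenic diet and vagus nerve stimulation) or changes in dosage", which covers a new AED. It then says that "any patients taking these medications after randomization should not be withdrawn from the study unless there are safety concerns", and leaves any effect on the primary endpoint to the evaluable period in 13.6.1.
- **Protocol 10** has a mandatory withdrawal list and a discretionary one. The discretionary list opens with "Patients may also be withdrawn from the study for any of the following" and contains the item "Addition of a new AED (blinded phase only". An adverse event that compromises safe participation is a separate item in the same list. The synopsis repeats the AED item under Criteria for Withdrawal.
- **Protocol 13.6.1** ends the evaluable period no later than the day before a relevant change in prohibited or AED medication.
- **SAP 5.1.3.4** defines the treatment period as Day 1 to Day 113, with no cut-off at an AED change. SAP 5.8, which lists changes to the planned analysis, does not mention the difference.
- **SAP 5.5.3.1.1** assesses blinded-phase response "for patients who have not withdrawn from the trial during the treatment period". For the extension it adds: "However, for the OLE periods, withdrawn patients may be considered responders". SAP 5.5.3.2.1 uses the same non-withdrawal condition for the 25%, 75% and 100% thresholds.
- **Protocol Table 13.6-1 and SAP Table 3** place the 50% responder comparison at tests 2 and 4 of a fixed sequence that stops at the first non-rejection.

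**The concern.** Adding an AED is an event after randomization that can itself reduce seizures. A plan should fix in advance how such a patient is scored. Here the score follows from whether the site withdraws the patient, and the protocol gives two different steers on that decision. Two patients with the same medication history and the same seizure counts can therefore be classified differently.

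The endpoint concerned is controlled for type I error. If test 2 is not rejected, tests 3 to 8 are not performed. Those include the primary endpoint for 50 mg/kg/day.

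**Working it through.** **1. Do the protocol passages conflict?** With a safety concern, 8.3 and 10 are compatible, since both allow withdrawal. Without one, 8.3 says to keep the patient and 10 permits withdrawal. The AED item in Section 10 cannot be read as carrying an unstated safety condition, because the safety ground is a separate item. No section states which takes precedence.

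**2. Does the decision change the analysis?** Take a patient with a reduction of at least 50% who adds an AED.

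| Site action | Blinded-phase responder status under SAP 5.5.3.1.1 |
|---|---|
| Kept to Day 113 | Responder; days on the new AED are counted |
| Withdrawn during treatment | Not a responder |

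The SAP phrase could also be read as removing withdrawn patients from the denominator. The ITT definition (SAP 5.2.2) and the contrasting sentence for the extension favour scoring them as non-responders. Under either reading, status depends on the site's decision.

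**3. Which patients are exposed?** SAP 5.5.2 averages seizures over all reported days in the period. Assume every day is reported. Let the AED start on Day d, with reduction r1 over the d − 1 days before and r2 over the 114 − d days from then on:

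R = [(d − 1) × r1 + (114 − d) × r2] / 113, with response if R ≥ 0.50.

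- r1 = 0 and r2 = 1 (baseline rate until the AED starts, seizure-free from then): 114 − d ≥ 56.5, so d must be 57 or earlier.
- r1 = 0.15 (the planning mean for placebo) and r2 = 1: 113 − 0.85 × (d − 1) ≥ 56.5, so d − 1 ≤ 66.5 and d must be 67 or earlier.
- r1 = 0 and d = 29: r2 must be at least 56.5/85 = 66.5%.
- r1 = 0.50 or more: any d qualifies if r2 is also at least 0.50.

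Exposure is therefore mainly to early additions and to patients already improving. Anyone who ends below 50% is a non-responder whether kept or withdrawn.

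**4. How large is the effect?** With the planned 70 patients per group, each reclassified patient moves an arm's rate by 1/70 = 1.43 percentage points.

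The documents give no expected responder rates and no number of AED additions. To gauge the margin, assume normally distributed percentage changes with the planning values in Protocol 13.1 (mean reductions 15% and 50%, SD 60%). The implied responder rates are Φ(−35/60) = 28.0% on placebo and 50.0% on active, about 20/70 and 35/70. An unstratified two-proportion z test, standing in for the age-stratified CMH test, gives:

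| Active vs placebo responders | p |
|---|---|
| 35 vs 20 | 0.009 |
| 35 vs 22 | 0.025 |
| 35 vs 24 | 0.060 |
| 33 vs 20 | 0.023 |
| 31 vs 20 | 0.053 |

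From that starting point, four reclassified patients in one arm are needed to lose significance at 5%. Fewer would be enough only if the observed result already lay close to the boundary.

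**The case against.** The strongest reply is that Section 10 is permissive. A new AED is not on the mandatory list, so a site that keeps the patient complies with both sections, and 8.3 can be read as the default. This stands as far as it goes: it would be wrong to infer that the two sections give contrary orders, or that Section 10 makes the patient a non-responder. It does not remove the problem, because a site that withdraws the patient can also cite the protocol.

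A second reply is that the protocol already handles the added AED through the evaluable-period cut-off. That is true of Protocol 13.6.1. The SAP, which governs the analysis, does not carry the cut-off over.

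Four stronger readings are tempting, and the documents do not support them:

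- *A poorly controlled patient who adds an AED around the middle of the period becomes a responder by being kept.* A patient at the baseline rate who becomes seizure-free from Day 60 reaches only 1 − 59/113 = 47.8% and is a non-responder either way.
- *One or two such patients would overturn test 2.* This needs responder counts chosen near the boundary, and no document figure supplies them.
- *The bias runs in a known direction.* More additions on placebo are plausible if the drug works, but no counts are given and sites decide under blind.
- *The same decision settles per-protocol membership, and affects the primary endpoint equally.* SAP 5.2.3 also excludes patients for deviations judged to compromise efficacy, so a kept patient may be excluded too. SAP 5.1.1.1 uses primary-endpoint data after withdrawal. The primary is therefore less exposed, although Protocol Appendix 4 reduces IVRS calls after withdrawal and fewer days may be available.

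**Conclusion.** The point holds in limited form. Where a new AED raises no safety concern, the protocol lets sites act differently. The SAP turns that difference into responder status on an alpha-controlled endpoint, and counts seizures on the new AED for patients who are kept. The inconsistency and the dropped cut-off follow from the text alone.

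The numerical effect is probably small: 1.4 points per affected patient, confined to patients who reach a 50% reduction over the period. It could decide test 2 only if the result were near the boundary. The four-patient margin rests on the planning means and SD, normality and an unstratified test. The number of AED additions and their split by arm are unknown. The change should be made because it is cheap and removes an avoidable dependence on site discretion; it does not suggest that the trial's conclusion is unsafe.

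**What to change.** 1. **Protocol.** Reconcile 8.3, 10 and the synopsis withdrawal criteria so that one rule on staying in or leaving the study applies at every site when a new AED is added in the blinded phase. Which rule that should be is a clinical matter and is not proposed here.
2. **SAP 5.5.3.1.1 and 5.5.3.2.1.** Make responder status independent of the site's decision: count a patient who starts a new AED during Day 1 to 113 as a non-responder, whether kept or withdrawn. This matches how the SAP already treats withdrawn patients. Truncating at the AED change is a reasonable alternative that the protocol already contains, so repeat the analysis with the 13.6.1 cut-off as a sensitivity analysis.
3. **SAP 5.1.3.4 and 5.8.** State whether the 13.6.1 cut-off applies and, if it does not, list this as a change from the protocol.

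The cost is one protocol clarification, a few SAP sentences and one additional analysis, settled before unblinding. Protocol 8.2 and 9.2.5 already require medication changes to be recorded on the CRF, so no new data are needed. Responder rates may be slightly lower.
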